*** Giving intervention:**

Formulas for estimating CVD risk in the future 10 years, ARR by antihypertensive treatments have been edited in the software of excel 2007. The corresponding risk probabilities can be simply obtained by imputing the values of the risk factors, such as age, gender, systolic blood pressure, total cholesterol, and BMI. Health educators will fill the information sheet, based on the calculated values, and then give the intervention by reading the individualized information on the sheet. The intervention will be given for twice by face-to-face and by telephone, respectively, with a gap of one week.

Health educators will be well trained before the study on (i) the explicit meaning of CVD risk and ARR by antihypertensive treatment, (ii) how to use the excel risk estimation tool, (iii) correctly filling the information sheet (see a sample in the attachment) and expressing the individualized information in an identical way as in the information sheet. They have to pass an exam of practice which includes all the aforementioned contents after the training. During the study, the intervention process and effects will be monitored in patients of the intervention group.

*** Blinding:**

(i) Patients will be blind to the hypothesis of the study, but not to their grouping status. In the informed section, they are only going to be told about the purpose of the study, but the expected direction of behavior changes will be held from the patients.

(ii) Doctors will be blind to patients' grouping status.

(iii) Health educators, interviewers and researchers in charge of data analyses will be aware about patients' grouping status.

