*** Follow-up:**

Title of project: Effects of individualized antihypertensive information on the medication use in hypertensive patients: An exploratory randomized controlled trial.
 Principle investigator: [name]

Interviewers will be in charge of patients' follow-up. Telephone interview will be conducted at two weeks, three months, and six months after the intervention. Patients in the control group will receive the individualized antihypertensive information in the last time follow-up. Contents of the survey include:

- (1) Medication use of antihypertensive treatments;
- (2) Life style changes;
- (3) Knowledge and attitudes to antihypertensive treatments;
- (4) Any possible contamination during the study, doctors' attitudes and the effects on patients decisions or behaviors.

6. Statistical analyses:

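### Interviewers who take the recalled primary outcomes by telephone, and the data analysts, are planned to know the allocation; masking both is a cheap, partial improvement

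*Combined protocol and SAP*

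**What the plan says.** The Blinding paragraph (section 5, Implementation of the study) sets out three levels. On patients: "Patients will be blind to the hypothesis of the study, but not to their grouping status". On clinicians: "Doctors will be blind to patients' grouping status". On the remaining staff: "Health educators, interviewers and researchers in charge of data analyses will be aware about patients' grouping status". No reason is given for the third.

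The Follow-up paragraph of the same section states "Interviewers will be in charge of patients' follow-up" and "Telephone interview will be conducted at two weeks, three months, and six months after the intervention". The first survey item is "Medication use of antihypertensive treatments". The survey also covers knowledge and attitudes, and possible contamination. The same paragraph adds: "Patients in the control group will receive the individualized antihypertensive information in the last time follow-up".

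Section 4, Outcomes of interest, defines the two primary outcomes: any antihypertensive medicine taken in the previous two weeks, and more than 80% of prescribed tablets taken in the previous week. Section 6, Outcomes analyses, names a longitudinal regression, with a mixed effects logistic model run in Stata. It names no primary time point among the three follow-ups, no covariates and no rule for missing data.

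**The concern.** The person who asks the outcome question, the person who answers it and the person who analyses the answer all know the arm. The protocol uses the term self-report only for life style, but medicine-taking asked about over the telephone is self-report as well. The protocol describes no pill count, refill check, fixed follow-up script or coded arm labels.

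The Hypothesis section expects the information to raise both rates. An interviewer who knows the arm can probe harder, or accept an answer more readily, in one arm than in the other. The likely direction favours that hypothesis. Once a coloured answer is recorded, no later analysis can recover the uncoloured one.

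The analysts' case is weaker but real. What section 6 leaves open (which follow-up is primary, how the model is specified, how missing interviews are handled) would be decided by people who can see which arm each choice favours.

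**Working it through.** **1. The chain of knowledge.** Setting the paragraphs side by side:

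| Role | Knows the arm? | Part in the primary outcomes |
|---|---|---|
| Patient | Yes; not told the expected direction | Gives the answer |
| Interviewer | Yes, by plan | Asks and records it by telephone |
| Data analyst | Yes, by plan | Sets what the plan leaves open and runs the model |
| Doctor | No | None described at follow-up |

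One planned step needs the allocation at follow-up: delivery of the deferred information to control patients at the last contact. The six-month outcome interview is that same contact. If the information is delivered separately, after the interview closes, the listed survey items can be asked without knowing the arm.

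**2. The plan's own sample size.** Blinding does not enter it; it is reproduced only to fix the arm size used below. With two-sided alpha 0.05 and power 0.80, (1.960 + 0.842)² = 7.849. The plan's formula with rates 0.75 and 0.55, mean 0.65, gives n = 2 × 7.849 × 0.65 × 0.35 / 0.20² = 89.28, so 90 per group, and 90 / 0.90 = 100 recruited. This matches the stated figures. (It does so only for a fall of 0.20; 0.75 against 0.95 gives 50.04. That is a separate matter.)

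**3. What a reporting difference would do.** Inputs from Sample size calculation: n = 90 analysed per arm; base rates 0.75 (treatment) and 0.40 (adherence). Assumptions: no true effect; the intervention arm over-reports by b relative to control; a two-sided 5% two-proportion test at one time point. The documents give no value for b, so a range is shown.

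With p the base rate, p₂ = p + b and p̄ = (p + p₂)/2:

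- SE₀ = √(2p̄(1 − p̄)/n)
- SE₁ = √((p(1 − p) + p₂(1 − p₂))/n)
- Rejection rate = Φ((b − 1.96·SE₀)/SE₁) + Φ((−b − 1.96·SE₀)/SE₁)

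Example, p = 0.75 and b = 0.05: p̄ = 0.775, SE₀ = 0.06225, SE₁ = 0.06214. The terms are Φ(−1.159) = 0.123 and Φ(−2.768) = 0.003, total 0.126.

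| Assumed total b | Base 0.40 | Base 0.75 |
|---|---|---|
| 0 | 5.0% | 5.0% |
| 0.02 | 5.9% | 6.1% |
| 0.05 | 10.4% | 12.6% |
| 0.10 | 27.0% | 38.8% |

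**4. What the table measures.** b is the whole reporting difference between arms. Part would come from patients who know their arm and part from interviewers; the documents give no way to divide it. The planned longitudinal model of change from baseline is also not this single-time-point test. The table shows sensitivity to reporting bias, not the gain from masking.

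**The case against.** This is an openly delivered behavioural intervention in a trial labelled exploratory, and its blinding status is disclosed without contradiction. Patients are not told the expected direction of change, which bears directly on biased answers. At baseline, medication use is recorded as numbers (dose each time, times per day, days in the past week) and prescriptions come from medical records. If follow-up repeats those items, which the Follow-up paragraph does not spell out, the 80% threshold is arithmetic rather than judgement. Patients may reveal their arm anyway. All of this stands, and it limits the point to prompting and probing and to a partial remedy.

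A reader might also infer more than the documents support:

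- *That interviewers have no use for the allocation.* As written, whoever handles the last follow-up contact needs it to give control patients their information. The protocol names interviewers and health educators separately but does not say that different people fill the roles.
- *That the intervention arm gets extra measurement contacts.* Giving intervention says "the intervention process and effects will be monitored in patients of the intervention group", at the end of a paragraph on educators' training and examination. This can be read as a check on delivery; no added contact or measurement is described.
- *That analysts are free to pick the cut-offs.* Section 4 fixes both windows and the 80% threshold, and S4 Table shows adherence at ten cut-offs from 10% to 100%.
- *That masking is nearly free.* That is fair for coding the arms. For interviewers it needs reordered questions and a separate call, and the documents give no staffing data.

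**Conclusion.** The point holds as an avoidable weakness in outcome ascertainment: planned awareness of the allocation among those who record and those who analyse recalled primary outcomes, with no reason given and no compensating safeguard described. It should be fixed. It is not a fatal flaw, because the remedy is partial and the intervention cannot be hidden from patients.

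The size attributable to unmasked interviewers and analysts cannot be computed from the documents. The illustrative rates (about 6%, 10-13% and 27-39% for total differentials of 2, 5 and 10 points) rest on the assumed differential, no true effect, 90 per arm and a simple two-proportion test. A reader might take them as the error that masking would remove, or as a sign that reported results are biased. Neither follows: masking removes an unknown share, and nothing in the documents shows that interviewers influenced any answer.

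**What to change.** Rewrite item (iii) of the Blinding paragraph so that, among study staff, only the health educators and the allocation nurse know the allocation. In support of that:

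- State that interviewers and health educators are different people.
- Give interviewers a call list without group and a fixed script, with medication questions first and knowledge and contamination questions last, so that any disclosure by the patient comes after the primary outcomes are recorded.
- Have a health educator give the control group's deferred information in a separate contact, after the six-month interview is closed.
- Have analysts work on arms coded A/B until the primary results are fixed.

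The cost is protocol wording, a revised call list and script, and one separate health-educator call per control patient (about 100 at the planned size). Sample size, alpha and power do not change. Some patients will still reveal their arm, and patients' own reporting bias remains.

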*** Follow-up:**

Title of project: Effects of individualized antihypertensive information on the medication use in hypertensive patients: An exploratory randomized controlled trial.
 Principle investigator: [name]

Interviewers will be in charge of patients' follow-up. Telephone interview will be conducted at two weeks, three months, and six months after the intervention. Patients in the control group will receive the individualized antihypertensive information in the last time follow-up. Contents of the survey include:

- (1) Medication use of antihypertensive treatments;
- (2) Life style changes;
- (3) Knowledge and attitudes to antihypertensive treatments;
- (4) Any possible contamination during the study, doctors' attitudes and the effects on patients decisions or behaviors.

6. Statistical analyses:

*** Sample size calculation:**

$$n = \frac{2(u_\alpha + u_\beta)^2 \bar{P}(1 - \bar{P})}{(P_1 - P_2)^2}$$

Inequality test for two proportions is applied in the calculation.

Sample sizes in two groups are assumed to be equal.

$\alpha = 0.05$ (For preplanned subgroup analysis: on/ not on antihypertensive drug therapy);

Power: $1 - \beta = 0.80$

Rate difference between groups: $\Delta P = 0.20$

Pharmacological treatment rate in control: $P_1 = 0.75$

$n_1 = n_2 = 90$

A total of 100 patients are going to be recruited in each group, when the rate of loss to follow up is assumed to be 10%.

This predefined sample size in each group is able to detect the difference of 0.20 in rate of good adherence between groups, with the significant level of 0.05, power of 0.80 and the baseline rate of 0.40.

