Our null hypothesis is that the individualized antihypertensive information will have no effects on the rate of treatment or the rate of good adherence in hypertensive patients in China. The alternative hypothesis is that this information will increase both rates.

Methods:

1. Design overview:

A two-site, randomized controlled trial is going to be conducted to compare the individualized antihypertensive information on the basis of life style suggestions and usual care with life style suggestions and usual care solely in hypertensive patients. Eligible patients will be randomly allocated to two paralleled study groups with a ratio of 1:1. Patients will know their groupings, but they will be blind to the hypothesis of this study. Doctors will be blind to patients' grouping status.

2. Settings and patients:

Sequential clinic patients who are eligible and agree to participate will be enrolled in two primary care centers in Longgang District, Shenzhen, Guangdong Province. Inclusion criteria of the study subjects are as follows:

- (1) Patients with primary hypertension;
- (2) Age range: 35-65 years old;
- (3) BP lower than 160/100mmHg at diagnosis, or systolic blood pressure lower than 145mmHg for patients already on antihypertensive medications measured in clinic at recruitment;
- (4) Patients have at least graduated from primary school;
- (5) No deafness, blindness, or dementia, have no difficulty in understanding the antihypertensive information and information in the questionnaire;
- (6) Residents in Shenzhen, patients have no plan to move to other cities or countries in the following 6 months;
- (7) Informed consents have been signed.

Patients with any one of the following conditions will be excluded from this study:

- (1) Patients with hypertensive emergencies and urgencies, which are judged by

Title of project: Effects of individualized antihypertensive information on the medication use in hypertensive patients: An exploratory randomized controlled trial.
 Principle investigator: [name]

-
- physicians in the primary care centers;
- (2) Patients with drug-induced hypertension, drugs include sympathomimetic agents, non-steroidal anti-inflammatory drugs (NSAIDs) and cyclooxygenase 2 (COX-2) inhibitors, corticosteroids, central nervous system (CNS) stimulants, estrogens and progesterone, dietary supplements, serotonin-norepinephrine reuptake inhibitors (SNRIs), immunosuppressants; (19)

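### The stated 90 per group does not follow from a control treatment rate of 0.75 and the hypothesised 20-point increase: the printed formula gives 51, and the second rate is never stated.

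*Combined protocol and SAP*

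**What the plan says.** Under Statistical analyses, Sample size calculation, the protocol prints the pooled-variance formula for two proportions and lists its inputs:

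- Control rate: "Pharmacological treatment rate in control: $P_1 = 0.75".
- Difference: 0.20, without a sign. No rate is given for the intervention arm.
- Alpha 0.05, with an unexplained note about a preplanned subgroup analysis by treatment status; power 0.80.
- Test: "Inequality test for two proportions is applied in the calculation". The number of sides is not stated.
- Result: 90 per group, raised to 100 for 10% loss to follow-up.

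The same paragraph says that this size also suffices for a 0.20 difference in good adherence from a baseline of 0.40.

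The Hypothesis section fixes the direction: "The alternative hypothesis is that this information will increase both rates". Treatment rate and rate of good adherence are both listed as primary outcomes.

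**The concern.** A control rate of 0.75 and an increase of 0.20 put the intervention arm at 0.95. The variance of a proportion shrinks near 1, so a rise from 0.75 needs far fewer patients than a fall of the same size. Under the printed formula the direction therefore changes n substantially, and 90 is not the figure for a rise.

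This paragraph is the trial's only statement of what it can detect on treatment rate. A reader who takes it at face value will think that 0.20 is the smallest rise detectable with 80% power, when the design can detect a smaller one. A reader also cannot tell which pair of rates the planners had in mind.

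**Working it through.** **Inputs.** From the sample-size paragraph: control rate 0.75, difference 0.20, alpha 0.05, power 0.80, equal groups. From the Hypothesis section: the direction is up. Two-sided testing is assumed from the words describing the test; one-sided testing is tried below.

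**Formula as printed.** n = 2 (u_alpha + u_beta)² × Pbar(1 − Pbar) / (P1 − P2)² per group. With u_alpha = 1.960 and u_beta = 0.842, the factor 2 (u_alpha + u_beta)² is 15.698. The denominator is 0.20² = 0.04.

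**Reproducing the plan's 90.** With rates 0.75 and 0.55, Pbar = 0.65 and Pbar(1 − Pbar) = 0.2275. Then n = 15.698 × 0.2275 / 0.04 = 89.28, rounded up to 90. The loss allowance also reproduces: 90 / (1 − 0.10) = 100.

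**The hypothesised increase.** With rates 0.75 and 0.95, Pbar = 0.85 and Pbar(1 − Pbar) = 0.1275. Then n = 15.698 × 0.1275 / 0.04 = 50.04, rounded up to 51.

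**Other readings, all at 80% power:**

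| Reading | 0.75 and 0.95 | 0.75 and 0.55 |
|---|---|---|
| Printed formula, two-sided 0.05 | 50.0 | 89.3 |
| Printed formula, one-sided 0.05 | 39.4 | 70.3 |
| Printed formula, two-sided 0.025 | 60.6 | 108.1 |
| Separate null and alternative variances (Fleiss), two-sided 0.05 | 49 | 89 |
| The same with continuity correction | 59 | 98 |
| Unpooled variance, two-sided 0.05 | 46.1 | 85.4 |
| Arcsine, two-sided 0.05 | 44.2 | 87.6 |

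No variant brings 0.75 to 0.95 near 90.

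**Two ways to 90 that depart from the stated inputs.**

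1. The formula is symmetric in the two rates. Control 0.55 and intervention 0.75 give the same 89.28, and in the hypothesised direction.
2. Using 0.75 as Pbar itself with two-sided alpha 0.025 gives 89.11. This conflicts with the stated alpha and with the label of 0.75 as the control rate.

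**What 90 evaluable per group can do if 0.75 is the control rate.** The power approximation is z = [0.20 √n − 1.960 √(2 Pbar(1 − Pbar))] / √(P1(1 − P1) + P2(1 − P2)).

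- 0.75 to 0.95: z = (1.897 − 1.960 × 0.505) / 0.485 = 1.87, so power is 0.969.
- 0.75 to 0.55: z = (1.897 − 1.960 × 0.675) / 0.660 = 0.87, so power is 0.808.
- Smallest rise from 0.75 at 80% power, solving the printed formula for n = 90: about 0.157, to about 0.907.

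**Good adherence, 0.40 to 0.60.** Pbar = 0.50, so n = 15.698 × 0.25 / 0.04 = 98.11 (Fleiss: 97). Power is 0.770 at 90 per group and 0.812 at 100.

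**The case against.** The strongest reply is that the paragraph makes no false claim. The difference is unsigned and the test is an inequality test, so 90 per group give at least 80% power for a 0.20 difference either way: 0.81 for a fall and 0.97 for a rise. Taking the larger n would be prudent. A null result would in any case be read from its confidence interval, and the appended sensitivity tables do report intervals. The title also calls the trial exploratory.

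Much of this stands. The discrepancy does not weaken the trial on this outcome, and it changes no analysis or recruitment figure. It does not remove the conflict, though. The paragraph assigns 0.75 to the control arm, the Hypothesis section says the rate will go up, and those two statements with the printed formula do not give 90. Nothing in the text says that the larger of two directions was chosen on purpose.

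A reader might go further and infer that the trial was designed to detect a fall in drug use. The document does not support that: 0.55 appears nowhere in it and is only back-calculated, and a mislabelled arm explains 90 equally well. Nor does a rate of 95% require that no treated patient stops. If all 25 untreated patients per 100 started, 5 of the 75 treated could stop and the rate would still be 95%.

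**Conclusion.** The concern holds as an internal inconsistency. With 0.75 as the control rate, two-sided alpha 0.05 and power 0.80, the hypothesised increase needs 51 per group, not 90. As labelled, the inputs return 90 only for a fall to 0.55. Whether the intervention rate was miscalculated or the arm label was swapped cannot be determined from the document.

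The error is conservative for treatment rate, so severity is minor to moderate. The conclusion rests on the two-sided reading, which is the one that reproduces 90 from 0.75 and 0.55 at the stated alpha. The shortfall of 0.75 to 0.95 from 90 holds under every variant tried.

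Two further inferences should be resisted. The figure of 51 is no reason to recruit fewer patients, because good adherence, the other primary outcome, sets the higher requirement. And the directional hypothesis does not need to be rewritten: a directional expectation tested two-sided is common and not contradictory.

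**What to change.** Keep 100 per group. In the sample-size paragraph, state the rate assumed in each arm, which arm has 0.75, and that the test is two-sided if that was intended. If 0.55 was the intended control rate, correct the label; 90 then stands as printed.

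If 0.75 is the control rate, replace the statement with text such as:

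> With 90 evaluable patients per group, the trial has 80% power (two-sided 0.05) to detect a rise in treatment rate from 0.75 to about 0.91, and about 97% power for a rise from 0.75 to 0.95.

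Under either correction, add beside it:

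> For good adherence, a rise from 0.40 to 0.60 needs about 98 evaluable patients per group by the same formula; power is about 77% with 90 per group.

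The cost is the wording of one paragraph. Recruitment, analysis and hypothesis are unchanged.

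### The stated 80% power for a 0.20 difference in good adherence holds only if all 100 recruits per group are analysed; after the plan's own 10% loss it is about 77%

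*Combined protocol and SAP*

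**What the plan says.** Section 6, Sample size calculation, uses a formula for comparing two proportions and describes the test in one line: "Inequality test for two proportions is applied in the calculation". For the treatment rate it takes a control rate of 0.75, a difference of 0.20, alpha 0.05 and power 0.80, and arrives at 90 per group. It then states "A total of 100 patients are going to be recruited in each group", on the assumption that 10% will be lost to follow-up.

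Good adherence gets one further sentence: "This predefined sample size in each group is able to detect the difference of 0.20 in rate of good adherence between groups". The conditions attached to that claim are alpha of 0.05, 80% power and a starting rate of 0.40. No separate sample size, loss allowance or intervention-group rate is given for it.

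Two other places bear on the reading. Section 4 lists good adherence as a primary outcome. The Hypothesis section sets the direction: "The alternative hypothesis is that this information will increase both rates".

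**The concern.** The adherence sentence follows directly on the recruitment figure of 100 and appears to credit the trial with 100 analysable patients per group. Yet the plan has just assumed that 10 of every 100 will be lost. Both primary outcomes come from the same telephone follow-up, so a loss allowance made for one applies to the other.

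At stake is the accuracy of a power figure stated for a primary outcome. Anyone interpreting a null adherence result would take the type II error to be 20% when, on the plan's own inputs, it is about 23%.

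**Working it through.** **Inputs.** From Sample size calculation: the formula n = 2(u_α + u_β)² · P̄(1 − P̄) / (P1 − P2)² per group, alpha 0.05, power 0.80, adherence baseline 0.40, difference 0.20, 90 per group needed, 100 recruited, 10% loss. From Hypothesis: the effect is an increase, so adherence is 0.40 versus 0.60 and P̄ = 0.50.

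**Step 1: reproduce the plan's 90, to settle sidedness.** The plan does not say whether alpha is one-sided or two-sided. With two-sided 0.05, (1.960 + 0.842)² = 7.849.
- Treatment rate 0.75 vs 0.55, P̄ = 0.65: 2 × 7.849 × 0.2275 / 0.04 = 89.3, so 90. This matches.
- Treatment rate 0.75 vs 0.95, P̄ = 0.85: 2 × 7.849 × 0.1275 / 0.04 = 50.0. No match.
- One-sided 0.05 with the same formula: 70.3 (0.75 vs 0.55) or 39.4 (0.75 vs 0.95). No match.

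Two-sided 0.05 is therefore the better inference. The match is not unique: P̄ = 0.75 with two-sided 0.025 gives 89.1. But the plan states 0.05, and the stricter level would lower adherence power further.

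With loss: 90 / 0.9 = 100, the plan's recruitment figure.

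**Step 2: sample size needed for adherence.** 2 × 7.849 × 0.25 / 0.04 = 98.1, so 99 evaluable per group. At 98 the formula gives 0.7995, just short.

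**Step 3: power for adherence.** Power = Φ(0.20 / √(2 × 0.25 / n) − 1.96).

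| Analysed per group | Calculation | Power |
|---|---|---|
| 100 (no loss) | Φ(2.828 − 1.960) | 0.807 |
| 90 (after 10% loss) | Φ(2.683 − 1.960) | 0.765 |

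Other methods at 90 per group agree: 0.770 with the Fleiss variance, 0.771 by the arcsine method, and 0.756 for the exact power of the uncorrected chi-square test.

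**Step 4: what 90 per group can detect.** For 0.40 vs 0.61, P̄ = 0.505: Φ(0.21 / √(2 × 0.249975 / 90) − 1.96) = Φ(0.858) = 0.80. The increase detectable at 80% power is about 0.209.

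**Step 5: recruitment that would deliver the stated power.** 99 / 0.9 = 110 per group, or 220 in total, against the planned 200.

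**The case against.** **The sentence is true on its nearest reading.** If the predefined sample size means the 100 recruited, power is 0.807 and the stated 0.80 is right for that number. This stands as a description of where the figure came from. It does not rescue the claim, because the preceding sentence assumes 10% loss and the figure fails once 2 per 100 are lost.

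**The test might be one-sided.** The alternative is directional, and one-sided 0.05 would give 0.85 at 90 per group. But that level does not reproduce the plan's own 90. What stands is that sidedness is inferred and should be declared.

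**The direction might be downward.** The plan's 90 matches a fall in the treatment rate. By the same convention adherence would go from 0.40 to 0.20, which needs only 2 × 7.849 × 0.21 / 0.04 = 82.4, so 90 would suffice. The Hypothesis section contradicts that direction. What stands is that the intervention-group rate is not stated.

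**The planned analysis is a longitudinal model.** Outcomes analyses names a mixed-effects logistic model, in which patients lost late could contribute earlier visits. The plan gives no within-patient correlation and does not use the model in the sample size, so it cannot support 0.80. Equally, 77% is the power of a simple two-proportion comparison and not of that model.

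**More patients were enrolled.** The percentages in the S4 Table imply denominators of 107 and 103. These are achieved numbers and do not correct a planning statement.

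**The gap is small beside the uncertainty in the baseline rate.** The plan gives no source for 0.40. At 90 per group, control rates of 0.30 or 0.50 give power of 0.78, and 0.25 or 0.55 give 0.80. This stands and limits the weight of the point.

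**A stronger reading to resist.** A reader might infer that, because both rates are expected to rise, adherence sets the power of the trial's whole claim and a joint power should be quoted. The documents do not support this. No section requires both outcomes to succeed, and the null is worded as no effect on one rate or the other. A joint figure would also need a correlation between the tests, which appears nowhere, and an intervention-group treatment rate, which the plan does not state.

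**Conclusion.** The point holds as a minor correction of a stated figure. For an increase in good adherence from 0.40 to 0.60, the 90 per group left after the plan's own loss assumption give power of about 77% (0.765 by the plan's formula), not 80%. The cause is that the loss allowance made for the treatment rate was not carried over to adherence.

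This rests on three assumptions: a two-sided 0.05 test (inferred), an increase (from the Hypothesis section), and a simple comparison of two proportions (the plan's own basis for sample size).

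A reader might go further and infer that the trial is materially underpowered or its design unsound. The documents do not bear that out. The shortfall is 3 to 4 points, the detectable increase moves only from 0.20 to about 0.209, and the title calls the trial exploratory.

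**What to change.** Replace the adherence sentence in Sample size calculation with wording such as:

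> With 90 evaluable patients per group after 10% loss and two-sided alpha of 0.05, power is about 77% for good adherence of 0.40 versus 0.60, or 80% for 0.40 versus 0.61. Power of 80% for a 0.20 increase would need 99 evaluable patients per group.

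This also states the intervention-group rate (P2) and the direction of effect for adherence, which the plan leaves out, and declares the test two-sided.

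The cost is one sentence and a slightly less favourable stated power; no design feature changes. Keeping the 80% claim for a 0.20 increase would instead mean recruiting 110 per group, 20 more patients in total, which a shortfall of this size does not by itself require.
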